ISRCTN	International Standard Randomised Controlled Trial Number

LTCF	Long Term Care Facility
MARS	Medication Administration Record Sheet
MHRA	Medicine and Healthcare products Regulatory Agency
NHS	National Health Service
NICE	National Institute for Health and Clinical Excellence
PAAD	Probiotics for Antibiotic Associated Diarrhoea
QA	Quality Assurance
QALY	Quality-adjusted Life Years
QoL	Quality of Life
QP	Qualified Person
R&D	Research and Development
RCT	Randomised Controlled Trial
REC	Research Ethics Committee
RN	Research Nurse
RO	Research Officer
RR	Pooled relative risk ratio
SAE	Serious Adverse Event
SAR	Serious Adverse Reaction
SEWTU	South East Wales Trials Unit
SIS	Service User Information Sheet
SOP	Standard Operating Procedure
SmPC	Summary Product Characteristics
SMPU	St Mary's Pharmaceutical Unit
SSA	Site Specific Assessment
SU	Service User
SUSAR	Suspected Unexpected Serious Adverse Reactions
тм	Trial Manager
TMG	Trial Management Group
TSC	Trial Steering Committee

UHB University Health Board

1 Amendment History

Pre-ethical approval

Amendment No.	Protocol version no.	Date issued	Author(s) of changes	Details of changes made
01	2.0	04/04/2012	All listed as Chief Investigator, Co- Investigators and Trial Team	Provisional approval granted by REC, with recommended amendments included. (see details in protocol)
02	3.0	18/05/2012	All listed as Chief Investigator, Co- Investigators and Trial Team	Further justification on use of service Users with mental capacity as requested by REC, together with minor changes to information documents.

Post ethical approval

Amendment No.	Protocol version no.	Date issued	Author(s) of changes	Details of changes made
01	4.1	07/09/2012	All listed as Chief Investigator, Co- Investigators and Trial Team	 1)eligibility assessment to be carried out purely by the GP 2)changes to study schema for clarity 3)minor change to the exclusion criteria, removing the words "due to difficulty of administering probiotic" 4) SU without capacity already receiving a probiotic" added to exclusion criteria following ethics discussion. 5) the exclusion criteria that the SU will be assessed against and what procedures will take place for the GP to be able to assess capacity if unable to carry this task out at time of antibiotic prescription. 6) Unblinding procedure simplified to reflect if there is a need to un-blind the SU for any reason, to contact the Study

	team
	7) Changes to screening, enrolment & randomisation logs to capture progression through the study; time point is anonymised; only care home will have a full list with names;only an anonymised list will be sent to SEWTU.
	8) Removal of "A withdrawal CRF will be completed at the end of the 8 week follow up period".
	9) Details of how to administer the study medication
	10) Updated explanation on how the study medication will be supplied, requested, stored, reconciled and disposed.
	11) Dose modification for toxicity changed "to reduce the daily intake to half to allow for adjustment. If the participant continues to be uncomfortable the study medication should be stopped."
	12) monitor AEs and SAEs for the 8 week follow up period (i.e. not 30 days after the last does of study medication)
	13)Vomiting and stomach pain have been removed from the known side effects
	14) GPs will not be responsible for reporting SAEs, the PI and care home nurses will be trained to deal with SAEs
	15) timeframe in which to get the samples to the lab stated; another sample should be taken if diarrhoea continues for 48 hours
	16) Removal of the sentence, "From literature, probiotics are known to carry some risks, including use in patients with cancer, diabetes, broad spectrum antibiotic therapy, septicaemia, organ transplantation and abscess. The medical history will be considered in light of these risk factors, by the Research

				Nurse at the initial consenting time point, while the GP will consider these risk factors in light of the medical history of the SU at the point of randomisation." 17) Paragraph added to state that regular monitoring will take place 18) Care home staff not to witness (sign/date) consent form, research team to witness consent 19)Professional legal representative should not be participants own GP if that GP is involved in running or managing the care home
02	4.1	07/09/2012	All listed as Chief Investigator, Co- Investigators and Trial Team	Minor amendments to the patient information sheets to reflect changes to the protocol

2 Synopsis

Short title	The Probiotics for Antibiotic Associated Diarrhoea (PAAD), a randomised controlled trial		
Acronym	PAAD Stage 2 RCT		
Internal ref. no.	SPON1069-11		
Clinical phase	III		
Trial design	A multi-centre double-blinded placebo-controlled two arm individually randomised trial of the effect of probiotics on AAD in SUs of care homes.		
Trial participants	Adults who are usually resident in participating nursing or dual-registered care homes in the UK who are prescribed antibiotics during the study period.		
Planned sample size	400 SUs (200 per arm)		
Follow-up duration	SUs will be followed up for eight weeks from the date of randomisation.		
Planned trial period	24 months		
Primary objective	To compare the effectiveness of probiotics vs. placebo, taken in conjunction with antibiotics, on the incidence of AAD in care home SUs.		
Secondary objectives	• To compare the effectiveness of probiotics vs. placebo, taken in conjunction with antibiotics, on the duration and severity of AAD in care home SUs.		
	• To compare the effectiveness of the probiotics vs. placebo in reducing the incidence of C. difficile -associated diarrhoea (CDAD) in care home SUs.		
	• To evaluate the impact of probiotics on Quality of Life (QoL) in care home SUs.		
	• To evaluate the cost effectiveness of probiotics for AAD in care home SUs.		
Primary endpoint	Occurrence of at least one episode of AAD during the eight weeks following randomisation.		
Secondary endpoints	 Proportion of stool samples positive for Clostridium difficile toxin A or B from SUs who develop AAD during the eight week follow-up period. Duration, frequency and recurrence of AAD during the eight-week follow-up period. QoL, measured using EQ-5D at the time of randomisation and each week during the eight-week follow-up period. Recovery from illness that triggered antibiotic treatment. Healthcare Resource Use, including GP and practice nurse consultations, other medication, procedures, investigations, hospital appointments, A&E attendances and any hospital inpatient admissions, measured at the end of the eight-week follow-up period. Upplanned hospitalisations, including all-cause and AAD related, during 		

	 the eight-week follow-up period. Adverse Events: e.g. vomiting, abdominal pain, excessive flatulence, bloating, skin rashes, during the eight-week follow-up period. Adherence to the antibiotic, probiotic/placebo treatment course. All causes of mortality in the 8 week follow up period.
Investigational	• VSL# 3, freeze dried lactose free sachet containing 4.4g of a mixture of
medicinal products	450 billion live lactic acid bacteria and bifidobacteria. These bacteria
	consist of eight strains of potentially beneficial bacteria:
	• Streptococcus thermophilus,
	• Bifidobacterium breve,
	 Bifidobacterium longum,
	• Bifidobacterium infantis,
	 Lactobacillus acidophilus,
	 Lactobacillus plantarum,
	 Lactobacillus paracasei
	• Lactobacillus delbrueckii subsp. Bulgaricus.
	Placebo Formulation (TBC): A lactose free powder 4.4g Sachet, matched for taste, consistency and colour. Dispensed as above.
Form	Freeze -dried powder
Dose	One sachet (4.4g of freeze-dried powder), twice daily
Route	Per oral

3 Study summary & schema

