5.2 Secondary objectives

- To compare the effectiveness of probiotics vs. placebo, taken in conjunction with antibiotics, on the duration and severity of AAD in care home SUs.
- To compare the effectiveness of the probiotics vs. placebo in reducing the incidence of *C. difficile*-associated diarrhoea (CDAD) in care home SUs.
- To evaluate *th*e impact of the probiotics on Quality of Life (QoL) in care home SUs.
- To evaluate the cost effectiveness of probiotics for AAD in care home SUs.

6 Study design

This is a phase III individually randomised, double-blinded, parallel group trial of probiotic versus placebo for care home SUs who are prescribed antibiotics for acute infection. A total of 400 SUs from approximately 24 care homes in Wales (and potentially England) will be randomised.

The target population are SUs resident in care homes under a long-term care plan. Data entry, management and analysis will be conducted centrally at the South East Wales Trials Unit (SEWTU).

7 Centre and Investigator selection

Care homes located in Wales and if necessary from the South West and other parts of England will be approached to take part in the PAAD Study. We will seek agreement about participation in the study from the manager and the owner of suitable care homes. An agreement, detailing roles and responsibilities will be signed by the care home manager and the owner of the care home. The care home manager will be defined as the Principal Investigator (PI) at the care home, as the study site, and by Cardiff University as the sponsor of the study.

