13.4.6 Stool sampling

Diagnostic stool samples will be collected only at times when diarrhoea occurs during follow up and a second sample will be collected if diarrhoea continues for greater than 48 hours. Diarrhoea, for the purposes of this study, is defined as 3 or more loose stools at BSC type 5 – 7, in a 24 hour period, following a period of normal stool consistency. Sampling will be carried out by a CHS / study research nurse. The sample will be put into containers provided by the study team. This container must be labelled with the participants ID number, initials and date of birth and sent by 1^{st} Class Royal Mail using Post Office approved SafeboxesTM, a method that meets legal requirements. The sample must be sent within 48 hours of taking the sample, in order to be analysed within 72 hours. The sample will be sent to the Public Health Wales Microbiology laboratory for the determination of microbial content, speciation of *C. difficile* culture, toxins A and B and as well as screening for carriage of antibiotic resistant bacteria. Any cultured *C. diff* isolates will be ribo-typed, toxin tested, and have antimicrobial sensitivity testing done, as well as screening for carriage of antibiotic resistant bacteria. All isolates will be retained and stored at -70°C.

The research team will receive results of study diagnostic stool sample analyses from the Microbiology laboratory.

		Defere	At time of	At time of antibiotic			F	ollow Up (wee	o Period ks)			
	Data Type	Berore study recruitment begins	consent	prescribed/ eligibility checked and confirmed	1	2	3	4	5	6	7	8
1.	Care Home	X										
2.	Eligibility for enrolment		Х									
3.	Eligibility for Study Medication			X								
	a) Medical information			X								
4.	Follow up diary											
	a) Study medication and antibiotic adherence				D	D	D	D				
	 b) Illness severity and symptoms 				D	D	D	D	D	D	D	D
	c) Stool monitoring				D	D	D	D	D	D	D	D
	d) Additional Medication				W1	W1	W1	W1	W1	W1	W1	W1
	e) Quality of life				W2	W2	W2	W2	W2	W2	W2	W2
	f) Healthcare resource use											E
5.	Diagnostic Stool Sample				I<			as req	uired			>l
6.	Withdrawal		I<			as	required					>l
7.	SAE				I<			as req	uired			>l

Table 1 – CRF schedule

D = Questions are to be completed on a daily basis

W1 = Questions should be completed on weekly basis for that week

W2 = Questions should be completed at the start of the week based on that day

E = Questions are to be completed at the end of the 8 week follow-up

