14.3 Secondary outcome measures

- The occurrence of *C.difficile*-associated diarrhoea (CDAD). This is defined as having a diagnostic stool sample (following the occurrence of AAD) that is found to contain *Clostridium difficile* toxin A or B.
- Health-related quality of life measured using the EQ-5D.
- The duration, frequency and recurrence of AAD. The duration of AAD is defined as the total number of consecutive 24 hour periods that a SU has AAD (as per our definition in 14.2.).
- The frequency of AAD is the number of episodes of AAD a SU experiences during the eight week follow-up period. AAD episodes are only considered unique if they are separated by a period of at least three days of "normal" stool consistency
- Recovery from the illness that triggered the prescription of antibiotic treatment. A single item will be asked daily and will capture the illness severity of the SU on a particular day
- Adherence to the study intervention and antibiotic treatment. Adherence will be defined as full (all doses on a particular day), partial (at least one dose but not all) and not (no doses on a particular day).
- Healthcare Resource Use. Costs will incorporate information on GP and practice nurse consultations, other medication, procedures, investigations, hospital appointments, A&E attendances and any hospital inpatient admissions and will be measured at the end of the eight-week follow-up period.
- Unplanned (not a routine hospital appointment) hospitalisation, both all-cause and AAD-related.

- Adverse events. These include reported symptoms such as vomiting, abdominal pain, excessive flatulence, bloating, skin rashes.
- All-causes mortality during the eight week follow-up period.

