14.4 Sample size

A total of 400 SUs (200 per arm) will need to be randomised in order to achieve 80% power, at the 5% level, to detect a 50% relative reduction in the incidence of antibiotic associated diarrhoea in those given probiotic intervention alongside antibiotic treatment, compared to placebo alongside antibiotic treatment. This sample size has been adjusted for a 20% loss to follow-up/withdrawal.

Taking into consideration the results from the interim analysis performed in PAAD Stage 1 and a more recent interim assessment of antibiotic prescribing and AAD (from first antibiotic prescription), assuming an AAD incidence of 25% in the placebo arm (lower confidence limit quoted in Appendix 3), in order to randomise 400 SUs we will need to obtain advanced consent from at least 607 SUs (assuming 66% will be prescribed at least one course antibiotics during the 12 month monitoring period and subsequently randomised) and will need to approach approximately 1214 SUs in order to achieve this consent rate (assuming only 50% will provide consent). With an average of 60 SUs per home, we will need to recruit from a minimum of 21 care homes. In order to allow for care home drop-out, larger than anticipated withdrawals/drop-out/declines and smaller than anticipated care homes, we aim to recruit from 24 care homes.

15 Analysis

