15.1.1 Secondary analyses

In a similar way to the primary analysis, a logistic regression model will be constructed, with 'Returned positive stool sample for *Clostridium difficile* toxin A and B following AAD' (YES/No) as the dependent variable and study arm (probiotic/placebo) as an explanatory variable, in order to investigate the effect of probiotics on the development of CDAD during the eight week follow-up period. In an analogous way to the primary, this analysis will adjust for clustering (if present) and confounding factors.

Generalised linear models will be used to order to:

- Investigate the effect of probiotics on the duration, frequency and recurrence of AAD during the eight week follow-up period
- Investigate the effect of probiotics on all-cause hospitalisations during the eight week follow-up period
- Investigate the effect of probiotics on illness recovery
- Investigate the effect of probiotics on antibiotic adherence
- Investigate the relationship between study intervention adherence and AAD/CDAD
- Investigate the relationship between antibiotic adherence and AAD/CDAD
- Investigate the effect of probiotics on mortality in the eight week follow-up period
- Investigate the effect of probiotics on both all-cause and AAD-related hospitalisation during the eight week follow-up period

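### The synopsis measures CDAD as the share of positive stool samples among residents with AAD, which conflicts with the incidence objective and with sections 14.3 and 15.1.1, and can hide a benefit or suggest a harm

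*Protocol*

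**What the plan says.** The secondary objective in section 5.2, repeated in the synopsis, is "To compare the effectiveness of the probiotics vs. placebo in reducing the incidence of" CDAD in care home residents. The protocol then describes the matching outcome in three places.

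- **Synopsis, secondary endpoints:** "Proportion of stool samples positive for" C. difficile "toxin A or B from SUs who develop AAD during the eight week follow-up period". The unit is the sample, and the denominator is samples from residents who had AAD.
- **Section 14.3:** the occurrence of CDAD. "This is defined as having a diagnostic stool sample (following the occurrence of AAD) that is found to contain" toxin A or B. The unit is the resident; the denominator is not stated.
- **Section 15.1.1:** a logistic regression, built similarly to the primary analysis, on a returned stool sample positive for "toxin A and B following AAD' (YES/No) as the dependent variable and study arm (probiotic/placebo) as an explanatory variable". The unit is the resident; the denominator is again not stated, and the toxins are joined by *and* where the other two places have *or*.

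On sampling, section 13.4.6 collects specimens only when diarrhoea occurs, and "a second sample will be collected if diarrhoea continues for greater than 48 hours".

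**The concern.** The synopsis endpoint differs from the objective in two respects.

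First, its denominator is the primary outcome. AAD arises after randomisation, and the trial is designed to show that the probiotic reduces it. Among residents who develop AAD the two arms are no longer the groups that randomisation made comparable. The share of AAD due to C. difficile depends on what the probiotic does to C. difficile and also on what it does to every other cause of AAD. Complete sample return would not remove this.

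Second, its unit is the sample. An episode beyond 48 hours yields a second specimen, so longer episodes weigh more. Duration of AAD is itself compared between arms, so the weighting may differ by arm.

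At stake is the answer to a named secondary objective. If the synopsis version were followed, a probiotic that reduces CDAD could appear to have no effect, and one that leaves CDAD unchanged could appear to raise it.

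**Working it through.** **Inputs**

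- Placebo AAD: "assuming an AAD incidence of 25% in the placebo arm" (section 14.4).
- Target effect: "to detect a 50% relative reduction in the incidence of antibiotic associated diarrhoea" (section 14.4), so 25% to 12.5%.
- Arm size: 200 randomised less 20% loss = 160 (section 14.4). It only turns percentages into counts; every percentage below is the same with 200.
- C. difficile share of diarrhoeal samples: 8 of 34 in Stage 1 (Appendix 2). Section 4.2 describes these as cultures, so using them for toxin positivity is an assumption. The range of 20–30% of AAD in section 4.1.3 serves as a sensitivity check.
- One sample per AAD case, a simplification that leaves out the double counting of long episodes.

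**The protocol's own figure:** 8/34 = 23.5%, which rounds to the stated 24%.

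**Placebo arm**

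- AAD cases: 0.25 × 160 = 40.
- CDAD cases: 40 × 8/34 = 9.4, or 9.4/160 = 5.9% of residents.
- Other AAD: 40 − 9.4 = 30.6.

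**Two measures**

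- Synopsis share = CDAD / (CDAD + other AAD); placebo 9.4/40 = 23.5%.
- CDAD incidence = CDAD / residents in the arm; placebo 5.9%.

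**Probiotic arm under five effects**

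| Effect of the probiotic | CDAD cases | Other AAD | Synopsis share (placebo 23.5%) | CDAD incidence (placebo 5.9%) |
|---|---|---|---|---|
| (a) CDAD and other AAD both halved | 4.7 | 15.3 | 4.7/20.0 = 23.5% | 2.9% |
| (b) CDAD alone halved | 4.7 | 30.6 | 4.7/35.3 = 13.3% | 2.9% |
| (c) Other AAD alone halved | 9.4 | 15.3 | 9.4/24.7 = 38.1% | 5.9% |
| (d) Total AAD halved, wholly through other AAD | 9.4 | 10.6 | 9.4/20.0 = 47% | 5.9% |
| (e) CDAD halved, other AAD cut by 75% | 4.7 | 7.6 | 4.7/12.4 = 38.1% | 2.9% |

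Row (d) requires other AAD to fall from 30.6 to 10.6, a cut of 1 − 10.6/30.6 = 65%. It is the more extreme case; row (c) is the plainer one.

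The last column depends only on what happens to CDAD. The share does not: rows (a), (b) and (e) have the same true halving of CDAD, yet show no difference, a benefit and an apparent harm.

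**Sensitivity to the placebo share, 20% to 30%**

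- (a): ratio of shares, probiotic to placebo, 1.00 throughout.
- (b): 0.56 to 0.59.
- (c): 1.67 to 1.54.

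The direction does not depend on the 23.5%.

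**The case against.** The strongest reply is that the body of the protocol already has the right outcome. Section 14.3 speaks of occurrence, section 15.1.1 models a Yes/No outcome by arm on the pattern of the primary analysis, and section 15.1 puts that analysis on the intention-to-treat principle. No section plans an arm comparison of sample proportions. On this reading the synopsis bullet is loose wording and nothing more.

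Much of this stands. A reader might infer that the planned CDAD analysis is itself conditioned on AAD; the protocol does not support that. It is not a complete answer, though. Neither 14.3 nor 15.1.1 states its denominator, and an outcome described as a positive sample following AAD can be read as restricted to residents with AAD, which is how the synopsis puts it. Section 15.1.1 also asks for toxins A and B where the synopsis and 14.3 ask for A or B.

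A reader might also infer that a halving of CDAD would always go unseen. It would not: if CDAD alone is halved, the share falls from 23.5% to 13.3%. The effect vanishes only when other AAD falls in the same proportion.

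Nor would an imbalance in the share necessarily be taken as harm. Even in row (d), whole counts of 9/20 v 9/40 give a Fisher exact p of 0.13. The objection to the endpoint is that it estimates the wrong quantity; it does not depend on a significant result.

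**Conclusion.** The concern holds as a contradiction between the synopsis and the rest of the protocol, in which the synopsis version is a biased measure of the objective. Followed as written, that version shows 23.5% v 23.5% when all AAD is halved evenly, although CDAD falls from 5.9% to 2.9% of residents. It shows 38.1% v 23.5% when only other AAD is halved and CDAD is unchanged. The sizes rest on 25% placebo AAD, the Stage 1 culture share in place of toxin positivity, and one sample per case; the directions hold over a placebo share of 20–30%.

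This is a defect in how a secondary endpoint is defined. It does not touch the primary outcome, and the analysis in section 15.1.1 is sound if all randomised residents are its denominator. It is worth correcting because the outcome answers a named objective and the body of the protocol does not fully settle the denominator.

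**What to change.** 1. Replace the synopsis bullet with the section 14.3 outcome: residents with at least one toxin-positive diagnostic sample following AAD within eight weeks, each counted once, out of all randomised residents.
2. State that denominator in section 15.1.1, so that residents without AAD count as No.
3. Reconcile toxin A or B (synopsis, 14.3) with toxin A and B (15.1.1).
4. Keep sample-level positivity as descriptive microbiology, without a comparison between arms.

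The cost is one synopsis bullet and a clarified sentence in 15.1.1, with no new data and no additional analysis. The correction removes the bias but does not make CDAD a well-powered outcome: for a halving from 5.9% to 2.9%, power is about 25% with 160 per arm and 30% with 200.
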